## 10.3 Dropouts and missing data management

Every case of dropout will undergo a complete analysis to avoid any bias. In case of missing data, the following procedure will be attempted:

- 1) Complete missing data by contacting GP/patient if feasible
- 2) Extrapolation if feasible
- 3) Exclusion of patient

## 10.4 Criteria for the termination of the trial

Termination is scheduled at most 9 months after index visit of the last patient included in the trial.

## **11. Ethics**

### **11.1 Relation to primary care practice**

The current study only aims to provide GPs an assistive tool to assess risk of cardiogenic chest pain. Moreover, each item of the CPR is known and already used in everyday practice to manage chest pain. We therefore believe that giving a defined weight to each of those items in order to help GPs' assessment should not alter in an unfavourable way GPs' behaviour and final decision regarding patient's complaint. It is important to note that the current CPR is not a decision rule and that it only incites GPs to take care of well-known and validated assessment criteria regarding chest pain.

### **11.2 Ethical committee**

The current protocol will be submitted to the cantonal ethical committee of Vaud, Lausanne, Switzerland.

### **11.3 Information and consent**

Each patient eligible for the study will be asked to participate at index visit. Patients agreeing to participate will get an information form to explain the purpose of the study and the modalities of follow up (see Annex 4, in French). They will be asked to sign a consent form and will be informed of their right to withdraw at any time of the study.

### **11.4 Confidentiality**

Confidentiality is guaranteed for each patient and GP taking part of the study. All the data collected are made anonymous by attributing a single code to each patient and GP so that it will not be possible to link medical information to patient's name and details. Patients agreeing to give a mobile phone number are informed that the number will not be kept after intermediate analysis.

## **12. Financing**

Financing will be requested at the RRMA commission of the Swiss Academy of Medical Sciences. Other sponsors may be contacted later on according to financial needs.

## **13. Registration**

This study will be properly registered to competent regulatory authorities in expectation of an eventual publication.

## **16. Appendices**

Annex 1: General practitioners' intensive training

Annex 2: Case report form (in French)

Annex 3: Questionnaire for intermediate analysis and end of follow-up (in French)

Annex 4: Information form for subjects enrolled (in French)

## **General practitioners' intensive training**

Two members of research team will provide GPs' training. One trainer will meet every GP selected to use the cardiovascular CPR while the other will meet every participating GP of the usual care group. Training at GP's office allows investigators to adapt to GP's schedule while a mandatory common training period at a defined date might have compromised participation.

We remember that in case of real implementation of the CPR, a personal training at the GP's office would not be feasible, but the content of the training would perfectly fit into seminars or congresses, within the context of the presentation of the current study for instance. We therefore believe that there is no major bias to expect and that meeting GPs at their own offices will only insure a higher participating rate.

### **Content of intensive training**

#### CPR group:

- The cardiovascular CPR is a new, simple and safe tool to rule out CHD in primary care patients complaining of chest pain when it is used in the proper way.
- The cardiovascular CPR has been especially developed for primary care and is only based upon patient's history and physical examination.
- Initial management of patient's complaint should not be modified. After first clinical evaluation, calculating the CPR provides extra information regarding the risk of cardiac origin to chest pain.
- Sensitivity, specificity, negative predictive value and negative likelihood ratio of the CPR.
- GPs should use the CPR to calculate the risk of cardiogenic chest pain, and only after that, decide whether they need to run complementary exams or not, depending on how the CPR reinforces their clinical impression.
- Decision to run further investigation remains to GP's judgment. The cardiovascular CPR is not a decision rule.
- In case of contradiction between clinical impression and CPR's result, GPs must pursue investigations. The cardiovascular CPR is derived from logistic regression and cannot identify unusual presentation (consider young patient who abuses cocaine for instance).

#### Usual care group:

- Investigators are running a new study about patients complaining of chest pain in primary care settings.
- The current study is a cluster-randomized trial.
- Some of the GPs get an intensive training before the trial while the others get the formation after the trial. They belong to the second group.
- The final purpose is to improve and facilitate the management of chest pain at GP's office.

## Première consultation

No patient :	No médecin :	Date :
--------------	--------------	--------

**Patient :** connu  / nouveau patient  sexe : F  / H  âge : \_\_\_\_\_ ans

**Consultation:** planifiée  urgence

**Lieu:** cabinet  à domicile  par téléphone   
autre  (préciser) : \_\_\_\_\_

### Douleur thoracique:

**Contexte :** nouvelle  / connue  plainte principale  / plainte secondaire

**Intensité:** faible  modérée  forte

[figure not shown]
**Installation:** soudaine  progressive

**Evolution:** en augmentation  en diminution  intermittente   
constante avec exacerbations

**Durée:** <1 minute  <15 minutes  <1 heure  heures   
jours  mal défini

**Type:** superficielle  profonde  oppressante  en lancées   
brûlure

**Localisation :** rétrosternale  transfixiante  localisée  étendue

Préciser (avec irradiation si présente) :

**Facteur déclenchant:** effort  mouvement  décubitus  repas   
anxiété  palpation

**Facteur aggravant:** toux  respiration  position  déglutition   
effort

Autre(s) caractéristique(s) (préciser) : \_\_\_\_\_

**Symptômes d'accompagnement :****Général :** fièvre  frissons  sudations  altération conscience **Cardiovasculaire :** palpitation  syncope  tachycardie  arythmie   
instabilité hémodynamique   
autre  (préciser) : \_\_\_\_\_**Respiratoire :** dyspnée  toux  expectorations   
autre  (préciser) : \_\_\_\_\_**Digestif :** dysphagie  reflux  épigastralgies   
autre  (préciser) : \_\_\_\_\_**Articulaire :** préciser si présent(s) : \_\_\_\_\_**Facteurs de risque :**HTA  diabète  dyslipidémie Tabagisme  : \_\_\_\_ UPA OH  : \_\_\_\_ dl/semaineAnamnèse familiale positive Antécédents personnels cardiovasculaires (maladie coronarienne, maladie cérébrovasculaire, artériopathie périphérique) Antécédent personnel maladie thromboembolique veineuse **Score clinique cardiovasculaire (uniquement pour les médecins du « groupe CPR ») :**

Swiss Heart Score	
Men over 55 years, women over 65 years	2 points
Known cardiovascular risk	2 points
Personal history of cardiovascular disease	2 points
Substernal pain	2 points
Duration of pain from 1 to 60 minutes	1 point
Increasing with effort	1 point
No tenderness at palpation	1 point
Total < 5 points: low risk of cardiogenic chest pain	
Total 5 to 7 points: intermediate risk of cardiogenic chest pain	
Total > 7 points: high risk of cardiogenic chest pai	
- Sensitivity 97.6%, specificity 71.3%, negative likelihood ratio 0.033, negative predictive value 99,5% (derivation cohort)	
- Sensitivity 85.6%, specificity 47.2%, negative likelihood ratio 0.305, negative predictive value 94.8% (validation cohort)	

**Total :** \_\_\_\_ points

Alternativement :

Marburg Heart Score	
Men over 55 years, women over 65 years	1 point
Known clinical vascular disease*	1 point
Pain worse during exercise	1 point
Pain not reproducible by palpation	1 point
Patient assumes pain is of cardiac origin	1 point
Total ≤ 2 points: low risk of cardiogenic chest pain	
* Coronary artery disease, occlusive vascular disease or cerebrovascular disease	
Sensitivity 89.1%, specificity 63.5%, negative likelihood ratio 0.17, negative predictive value 97.9% (results to be published)	

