### 1.2 Study clinical prediction rule

In order to help GPs rule out a serious cardiac condition in patients complaining of chest pain, several CPRs have been developed in the last few years, two of them in Switzerland (7, 8) and Germany (9, 10). They are only based on patient's history and physical examination and aim to define the risk of cardiac origin to chest pain.

The Swiss CPR allows points to each of the seven following items: known cardiovascular risk, men over 55 years or women over 65 years, personal history of cardiovascular disease, substernal pain (two points each), duration of pain from 1 to 60 minutes, increasing with effort, absence of tenderness at palpation (one point each). Cut-off point for the low-risk group is 5. This rule showed a sensitivity of 97.6% and a specificity of 71.3% in ruling out CHD, a negative likelihood ratio of 0.033 and a negative predictive value of 99.5% in the derivation cohort. External validation has been done using the cross-country cohorts and showed a sensitivity of 85.6% a specificity of 47.2%, a negative predictive value of 94.8% and a negative likelihood ratio of 0.305 for the Swiss CPR (N.B.: inclusion criteria in both German and Swiss studies were not the same, which may explain at least part of the difference between results of internal and external validation studies) (8).

German investigators have also run a further external validation study with a new cohort that confirms the validity of their CPR. The Marburg Heart Score showed a sensitivity of 89.1%, a specificity of 63.5%, a positive predictive value of 23.3%, a negative predictive value of 97.9%, a positive likelihood ratio of 2.44 and a negative likelihood ratio of 0.17. Germans also noticed that GPs whose clinical judgment was aided by the score showed a higher sensitivity (90.0 versus 82.9%) and specificity (66.8 versus 61.8) than those working without the score, but the difference was not

[figure not shown]
significant (11). More results should soon confirm safety and robustness of such CPRs, especially the final results and publication of the Marburg Heart Score.

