### 3.5 Data collected in the CRF

A case report form (CRF) has to be filled in by all the GPs for each patient included to define patient's characteristics, current pain, personal history of cardiovascular disease and risk factors. It will also provide investigators with information regarding complementary investigations, referrals or hospitalizations for each patient at the time of index visit.

GPs of the intervention group will be asked to calculate the risk of cardiogenic chest pain for each patient with the CPR. The CRF also includes questions directly addressed to GPs to appreciate use, satisfaction and acceptability of the CPR.

GPs who belong to the usual care group will have to evaluate the risk of cardiogenic chest pain according to their clinical judgement only.

As all the items of the CPR are part of usual practice (patient's history and physical examination) investigators will be able to calculate patients' risk of cardiogenic chest pain a posteriori in the usual care group with the data collected in the CRF.

[figure not shown]
(See Annex 2 for complete CRF)

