## 5. Study CPR

GPs selected to use the cardiovascular CPR as an assistive tool will have to calculate the risk of cardiac origin to chest pain for each patient. According to Gencer and al. (8), the Swiss CPR is the following:

Swiss Heart Score	
Men over 55 years, women over 65 years	2 points
Known cardiovascular risk	2 points
Personal history of cardiovascular disease	2 points
Substernal pain	2 points
Duration of pain from 1 to 60 minutes	1 point
Increasing with effort	1 point
No tenderness at palpation	1 point
Total < 5 points: low risk of cardiogenic chest pain	
Total 5 to 7 points: intermediate risk of cardiogenic chest pain	
Total > 7 points: high risk of cardiogenic chest pain	
- Sensitivity 97.6%, specificity 71.3%, negative likelihood ratio 0.033, negative predictive value 99.5% (derivation cohort)	
- Sensitivity 85.6%, specificity 47.2%, negative likelihood ratio 0.305, negative predictive value 94.8% (validation cohort)	

Except filling in the CRF and – for GPs allocated to the intervention group - calculating the risk of cardiogenic chest pain, taking history of the patient, examination, and further investigations have to be done as usual by GPs, according to their scientific knowledge and clinical experience.

Intensive training will provide GPs of the intervention group all information concerning aim, performance and limitations of the cardiovascular CPR as an assistive, prognostic tool (see Annex 1). Diagnosis and treatments should not be altered.

N.B. Investigators may choose to use the Marburg Heart Score instead of the Swiss Heart Score according to the not yet published results of Marburg's last external validation study. This will be decided before submission of the current protocol to the ethical committee.

Marburg Heart Score	
Men over 55 years, women over 65 years	1 point
Known clinical vascular disease*	1 point
Pain worse during exercise	1 point
Pain not reproducible by palpation	1 point
Patient assumes pain is of cardiac origin	1 point
Total ≤ 2 points: low risk of cardiogenic chest pain	
* Coronary artery disease, occlusive vascular disease or cerebrovascular disease	
Sensitivity 89.1%, specificity 63.5%, negative likelihood ratio 0.17, negative predictive value 97.9% (results to be published)	

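### The known-risk item of the Swiss score is undefined and scored by different people in each arm, so the low-risk groups compared in 10.2e may not be classed alike

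*Protocol*

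**What the plan says.** Protocol 1.2 gives the weights of the seven items, four of them worth 2 points: "known cardiovascular risk, men over 55 years or women over 65 years, personal history of cardiovascular disease, substernal pain (two points each". Section 5 repeats them in the score box, with "Known cardiovascular risk" and "Personal history of cardiovascular disease" on separate lines. A total below 5 is low risk, then "Total 5 to 7 points: intermediate risk of cardiogenic chest pain", and above 7 is high. Neither line carries a definition. The Marburg score printed in the same section does footnote its vascular-disease item.

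The case report form in Annex 2 has a block headed "Facteurs de risque". It lists hypertension, diabetes, dyslipidaemia, smoking, alcohol and family history, then "Antécédents personnels cardiovasculaires (maladie coronarienne, maladie cérébrovasculaire, artériopathie périphérique" and venous thromboembolism. The score box follows. No field is named after the known-risk item.

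The text of 3.5 and 10.2b names cardiovascular history and risk factors as two separate things. The training outline in Annex 1 covers the score's accuracy and how to use the result, but not the meaning of its items.

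Under 3.5, GPs in the intervention group calculate the score. Investigators can calculate it "a posteriori in the usual care group with the data collected in the CRF". Section 10.2c and 10.2d use the risk bands within the CPR arm. Section 10.2e compares low-risk patients between the arms and mentions retrospective calculation for usual practice only.

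**The concern.** A 2-point item with no definition matters when the low-risk cut-off is 5. The only place on the form from which the item can be scored also contains the box for another 2-point item. A GP working down the form may take a ticked history box as satisfying both lines, or only the history line. The protocol does not say which is meant, nor which or how many of the other boxes earn the 2 points.

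The ambiguity would be fairly harmless if one person scored everyone. Here the scorer differs by arm: many GPs at the visit in one, the research team working from the boxes in the other. If their conventions differ, the low-risk set in the CPR arm and the low-risk set in usual care contain different kinds of patient. A difference in tests or referrals under 10.2e could then partly reflect how patients were classed, or be masked by it. Section 4.1 expressly admits patients with known cardiovascular disease, so the patients concerned are in scope.

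**Working it through.** **Stated figures.** The plan gives no figure for this point. The one score statistic that can be recomputed from its own inputs is the negative likelihood ratio, (1 − sensitivity) / specificity. Validation cohort: (1 − 0.856) / 0.472 = 0.305, as stated. Derivation cohort: (1 − 0.976) / 0.713 = 0.0337 against 0.033 stated, a rounding difference. Nothing below depends on these.

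**Inputs (1.2, section 5).** Age/sex 2, known cardiovascular risk 2, cardiovascular history 2, substernal pain 2, duration 1, effort 1, no tenderness 1. The maximum is 4 × 2 + 3 × 1 = 11. Bands: below 5 low, 5 to 7 intermediate, above 7 high.

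**One patient.** A man over 55 with known coronary disease and no other risk box ticked; pain for days, not substernal, not effort-related, tender on palpation.
- History counted once: age/sex 2 + history 2 = 4, low.
- History also counted as known risk: 2 + 2 + 2 = 6, intermediate.

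**All item patterns.** Fix the history box as ticked and every other risk box as empty. The other five items (weights 2, 2, 1, 1, 1) give 2^5 = 32 patterns. With R the sum of those five, the total is 2 + R if history counts once and 4 + R if it counts under both lines.

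| R | Patterns | 2 + R | 4 + R |
|---|---|---|---|
| 0 | 1 | 2 low | 4 low |
| 1 | 3 | 3 low | 5 intermediate |
| 2 | 5 | 4 low | 6 intermediate |
| 3 | 7 | 5 intermediate | 7 intermediate |
| 4 | 7 | 6 intermediate | 8 high |
| 5 | 5 | 7 intermediate | 9 high |
| 6 | 3 | 8 high | 10 high |
| 7 | 1 | 9 high | 11 high |

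Low to intermediate: 3 + 5 = 8 patterns. Intermediate to high: 7 + 5 = 12. Unchanged: 1 + 7 + 3 + 1 = 12. Of the 9 patterns that are low when history counts once, 8 leave the low band when it counts twice.

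These are counts of item patterns, not of patients. A patient with a history who also has, say, hypertension scores both lines under either reading, provided hypertension counts as known risk. The documents do not say how many patients have a history and no other risk box ticked.

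**The case against.** A reader might infer that the score double-counts cardiovascular history, or that its two items overlap by design. The documents do not support that. The score lists two separate lines, and 3.5 and 10.2b keep history and risk factors apart. Double counting is only a reading that the form allows. The form is also seen here as extracted text, in which visual separation within the block may be lost.

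The derivation publication, cited as the source of the score, may define the item, and an analysis plan may fix the control-arm derivation. Neither would govern what a GP totals at the visit, which depends on the form and the training. The training is a real mitigation: section 3.1 says it is meant to make use of the score uniform, and Annex 1 has one trainer meet every CPR-arm GP. It could bring the GPs into line with one another. As outlined, though, it defines no items and does not tie the GPs' scoring to the investigators' derivation.

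Section 10.2e does not state outright that the CPR arm is classed by the GP's own total. It is the natural reading, because retrospective calculation is mentioned for usual practice only, but it remains a reading.

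Other extensions should be resisted. Scoring venous thromboembolism or alcohol as known cardiovascular risk is possible on this form but a weaker example than history. The protocol does not report that patients with known disease are tested or admitted more often, so the direction of any distortion cannot be argued from it. The score is also described as not being a decision rule, and GPs are told to pursue investigations when it contradicts their clinical impression.

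**Conclusion.** The point holds as a cheap improvement. One 2-point item is undefined, the form files a second 2-point item under the heading that would feed it, and the arms are scored by different people. For a patient with a history and no other risk box ticked, the band differs between the two readings in 20 of 32 item patterns (8 + 12), and in 8 of them it crosses the low-risk cut-off. The share of patients affected, and so any bias in 10.2e, cannot be derived.

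It would be tempting to conclude that the trial's main comparison is compromised. It is not: 10.2f compares whole arms without using the risk band. The reach is 10.2e between arms and 10.2c and 10.2d within the CPR arm.

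The conclusion assumes that the Swiss score is used and that the CPR arm's class in 10.2e comes from the GP's total. If the Marburg score is chosen, as section 5 allows, the item-definition part falls away. Which reading of the Swiss item is right is not judged here.

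**What to change.** For 10.2c to 10.2e, assign the risk class in both arms with one algorithm, written before the data are analysed, that maps the form's boxes to the seven score items. Keep the GP's total as the record of what the GP saw, and tabulate agreement between the two in the CPR arm.

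Separately, the investigators should reconcile section 5, the form and the training on which boxes score the known-risk item and whether a history alone also scores it. The form's layout should then follow from that decision; moving the history box beforehand would presuppose one answer.

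The cost is one derivation program, a sentence in section 5, a matching line on the form and a training point. There is a small downside: the analysed class will sometimes differ from the total the GP acted on, which is why agreement should be shown. The algorithm removes the difference in scoring rule between arms. It cannot remove any difference in how GPs tick the boxes.

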**Impression diagnostique :**

Suspicion maladie coronarienne : oui  / non

Degré de certitude : faible 0 – 1 – 2 – 3 – 4 fort

**Examens en urgence (effectués au moment de la consultation) :**

Aucune  ECG  Radiographie thorax  Test d'effort

Laboratoire: FSC  CRP  Troponines  CK   
BNP  D-dimères

Autre(s)  (préciser) : \_\_\_\_\_

**Suite de prise en charge :**

Aucune  Hôpital/Urgences

Consultation par cardiologue : délai <6 heures  <1 semaine  >1 semaine   
avis téléphonique

Consultation de contrôle au cabinet

Autre(s)  (préciser) : \_\_\_\_\_

**Appréciation du score clinique cardiovasculaire (uniquement pour les médecins du « groupe CPR ») :**

Utilisation *au cours* de la consultation :      oui  / non

*Sinon, pourquoi ?* Oubli       inadapté       autre  (préciser) : \_\_\_\_\_

Si le résultat du score a indiqué un *risque faible* d'origine cardiaque à la douleur thoracique :

Aucun impact      0 - 1 - 2 - 3 - 4      Rassurant

Degré de satisfaction : insatisfaisant      0 - 1 - 2 - 3 - 4      très satisfaisant

## Suivi à 3 et 9 mois

Questionnaire rempli par : infirmière de recherche (analyse intermédiaire à **3 mois**)   
 médecin (terme du suivi à **9 mois**)

No patient :	No médecin :	Date :
--------------	--------------	--------

### **Suivi du patient :**

Le patient a-t-il été revu *en raison de la douleur thoracique* **APRES** la consultation initiale :  
 oui  / non

*Si oui*, nombre de consultations ultérieures en lien avec la douleur thoracique : \_\_\_\_

### **Investigations complémentaires de la douleur thoracique (réalisées APRES l'inclusion dans l'étude) :**

Aucune

ECG de contrôle  *Si oui*, nombre : \_\_\_\_

Laboratoire  *Si oui*, nombre : \_\_\_\_

Radiographie thorax  *Si oui*, nombre : \_\_\_\_

Test d'effort

Autre  (préciser examen et nombre) : \_\_\_\_\_

